During the WBV, physicians will review the information provided by the woman on the RLPT about general health, reproductive plans, and use of contraception. The pediatrician will use the RLPT to initiate a brief conversation with mothers about the need for a referral for well-woman primary care. We expect this conversation to take less than 3 minutes based on previous studies.²² We will create a referral process to the UIH Primary Care Plus clinic (internal medicine) through our electronic medical record. At the close of the WBV, if the mother desires a referral the pediatrician can request the referral during the infant's check-out process. Research staff will routinely review all referral needs and initiate scheduling based on the mother's preference. Women will be asked if they prefer the **next available** appointment or an appointment on the **same day as their infant's next WBV**. For women who desire their health care visit on the same day as their infant's next WBV (the 4-month visit), we will schedule both visits on the same day. To the extent possible, the mother's appointment will be earlier the same day (ideally 2 hours before) of the infant's scheduled visit, to promote attendance. We expect that by offering women the opportunity for a primary care visit on the same day as their infants' next WBV, the likelihood of adherence will be much greater than just offering a referral. Among women scheduled for care, if by the date of their infant's next WBV the woman has not attended her visit (she cancels or does not show), the research staff will contact her to reschedule, offering either the first available appointment or co-scheduling with the infant's next WBV.

Reproductive Life Planning Tool: We have created a RLPT (in English and Spanish) based on detailed feedback from physicians and women regarding how best to operationalize a RLPT in the pediatric setting (previous research studies).

Study site: The CYC and PCAC are comprehensive pediatric clinics; patients can be seen by a pediatric faculty member (faculty practice) or by a pediatric resident physician with direct supervision by a faculty member. The clinics serves a predominantly low-income Medicaid-insured population.

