Though this is a system-level intervention, the intervention is targeting only the 2-month WBV, thus we do not expect a RLPT will be offered to a woman more than once. After consent is obtained, the RA will cross-check the participant list using a secure network on a tablet device to ensure that the woman is not already enrolled. Each RLPT will be linked to the infant by medical record number and date of birth. Limited physician characteristics (male/female, trainee/faculty) will be recorded; no physician names will be collected. The RLPTs for women who are consented and enrolled in the study will remain intact and all data will be collected from the tool and linked to the enrolled mother. The RLPTs for women who are *not* enrolled into the study will be de-identified after the Edinburgh tool is scanned by removing and shredding the patient sticker so no identifying information remains on the form. This will allow us to calculate clinic-specific adoption rates and examine the extent to which provider and system characteristics, such as the type of physician (e.g., attending versus resident), demographic characteristics of the physician (e.g., sex), and clinic operational factors (e.g., morning versus afternoon clinic; day of the week), influences adoption of the intervention (Table 1).

Consent for Intervention Group: Informed consent will be obtained for: 1) a baseline survey; 2) a phone survey at 6 months PP; and 3) access to a woman's medical records to document receipt of health care services. Women will be reimbursed for their time with gift cards [\$10 at baseline and \$10 at 6 months]. The RA will log the recruitment process, including number of women approached and if women accepted or refused, participation.

Pediatrician Training: Pediatricians (faculty and resident physicians) will all receive a 1-hour formal training on using the RLPT prior to the start of the study, offered at three different times to accommodate physician schedules. Research staff will touch-base

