with pediatricians weekly during the first 4 weeks of the study, and monthly thereafter, to answer questions and encourage consistent provider use of the tool. We will schedule a ‘refresher’ training 3 months after the start of the study to reinforce appropriate use of the tool. During the training, physicians will be instructed on how to start a conversation with women, what to document on the tool, and how to initiate a referral if needed. Physicians are *not* expected to provide contraceptive counseling to mothers, only to engage women in a discussion about their health care needs. An information sheet about the study will be given to all pediatric providers who are trained.

Selection of control group: The control group will be enrolled during phase 1 (first 4 months) prior to the introduction of the intervention. Similar to the intervention group, women will be recruited by an RA before, during or after the health care visit and screened for eligibility. Informed consent will be obtained for a baseline survey using the same procedure as described for the intervention group (same gift card amounts). Because we are studying health behaviors, we cannot share the specific aims of the study with control group participants as this could bias behavior. The control group participants will be told that this is a study monitoring women’s general health care experiences at UIH. After enrollment of the control group, a 6-week washout period prior to phase 2 (intervention) will ensure women are not enrolled into both arms of the study.

Sample: This pilot study will enroll at least 50 women per group. This sample size will provide a stable estimate of the intervention’s effect on primary care receipt by 6 months postpartum for power calculations for a larger, subsequent study of intervention effectiveness. There are approximately 200 deliveries per month at UIH, with 57% (114) of these infants having a 2-month WBV at UIH. For the 4-month period of recruitment each for control and intervention groups, we can meet our target enrollment of 50 in each group by recruiting women during four of the ten half-day CYC clinics per week, assuming a conservative participation rate of 40%.

Table 1 Study Variable Table

Variable	Specific Aim	Level of Measurement	Time of Collection	Tool	Variable Type
Demographic Data	I	Women	Enrollment	Baseline survey	Covariate
Physician Characteristics Male/Female, Trainee/Faculty	II	Physicians	Enrollment	Medical record schedule	Covariate

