Specific Aim II: Patient and physician facilitators, barriers and satisfaction data will be gathered from the RLPT, surveys, and focus groups. System adoption will be defined as the number of completed RLPT forms clinic-wide during the intervention (for enrollees and non-enrollees) divided by the total number of eligible visits during that time period, which will be ascertained through the clinic's scheduling database. Adoption will be compared across provider (e.g., status) and clinic operation factors (e.g., day of week) using chi-square tests. Adoption statistics will be shared with providers prior to focus groups, allowing them to elaborate on these findings. Qualitative focus group data from providers will be coded according to domains and analyzed for emergent themes related to feasibility and acceptability. Women's perceptions of feasibility and acceptability will be derived through the survey data and will be analyzed by other key covariates.

Although the findings of this study will reflect the experiences of low-income women at one large medical center in Chicago, they are likely to be relevant to the experiences of many low-income women. While a hospital outpatient clinic is a unique health care setting, the experience of having a pediatrician discuss new mothers' health needs and refer them for their own care is likely to be similar across pediatric practices. This study will add to the emerging literature related to a dual care focus for mother and infant. If this intervention is successful, it will provide evidence of the feasibility of introducing a system-level intervention related to women's health into pediatric practice. This information can inform changes in payment and policy to support the ability of pediatricians to discuss women's health needs and facilitate referral with mothers at their infants' WBV, with the ultimate goal of increasing women's use of primary care and PP contraception, preventing rapid repeat and unintended pregnancies, and ultimately decreasing adverse pregnancy outcomes.

References

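### Adoption is to be compared by chi-square tests alone, so if physician type overlaps with clinic scheduling, a scheduling effect could be read as a physician effect

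*Combined protocol and SAP*

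**What the plan says.** The combined protocol and SAP states the purpose under Participant Recruitment into the Research Study. De-identified forms from women who are not enrolled are kept so that the team can examine how physician type (attending or resident), physician sex and "clinic operational factors (e.g., morning versus afternoon clinic; day of the week), influences adoption of the intervention".

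The method is in Analysis, Specific Aim II: "Adoption will be compared across provider (e.g., status) and clinic operation factors (e.g., day of week) using chi-square tests". The results then go to providers before the focus groups, so that they can comment on them.

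No other analysis of adoption by these factors is described. Table 1 marks physician characteristics and clinic operations as Aim II covariates, but no Aim II analysis uses them together. The logistic model with average marginal predictions, under Specific Aim I and Ia, has the care visit and contraceptive use as its outcomes, not adoption.

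On staffing, the Study site paragraph says only that "patients can be seen by a pediatric faculty member (faculty practice) or by a pediatric resident physician with direct supervision by a faculty member". No timetable by session, weekday or clinic is given. On physician data: "Limited physician characteristics (male/female, trainee/faculty) will be recorded; no physician names will be collected".

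**The concern.** The stated purpose is to find what influences adoption, and a chi-square test on one factor cannot separate that factor from others that vary with it. Suppose faculty see more of their patients in the morning and residents more in the afternoon, and forms are completed less often in the afternoon. Residents would then show lower adoption even if physician type made no difference. The problem lies in the contrast itself, so better standard errors would not remove it.

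What is at stake is interpretation. A resident-faculty gap that is really a scheduling gap would be put to the physicians as a finding and could colour what they say in the focus groups.

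**Working it through.** **The plan's own figure.** The Sample paragraph states: "There are approximately 200 deliveries per month at UIH, with 57% (114) of these infants having a 2-month WBV at UIH". 200 x 0.57 = 114 per month, which reproduces. Over four months, 114 x 4 = 456 visits. This assumes that adoption is counted over the 4-month recruitment period and that all these visits are eligible.

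**Size of the spurious difference.** With no physician effect, the expected crude difference is

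(morning adoption - afternoon adoption) x (faculty morning share - resident morning share).

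It is zero if either bracket is zero.

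**Assumptions (none is in the documents).** Two-sided alpha 0.05; half of visits with faculty; morning adoption 80%; afternoon adoption lower by 0, 10 or 20 points; morning share of faculty and resident visits 50/50, 60/40, 70/30 or 90/10; visits independent. There were 20,000 simulated runs per setting with 456 visits. The table gives the spurious difference, then how often the chi-square test for physician type gives p<0.05.

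| Morning share, faculty/resident | No session gap | 10-point gap | 20-point gap |
|---|---|---|---|
| 50/50 | 0 points, 5% | 0 points, 5% | 0 points, 5% |
| 60/40 | 0 points, 5% | 2 points, 8% | 4 points, 16% |
| 70/30 | 0 points, 5% | 4 points, 16% | 8 points, 46% |
| 90/10 | 0 points, 5% | 8 points, 50% | 16 points, 96% |

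A Mantel-Haenszel test stratified by session rejects in about 5% of runs in every cell.

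**Check of one cell (70/30, 20-point gap).** Faculty: 0.7 x 0.80 + 0.3 x 0.60 = 0.74. Residents: 0.3 x 0.80 + 0.7 x 0.60 = 0.66. A standard two-proportion power calculation with 228 visits per group also gives 46%.

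**Second set of assumptions.** Residents see 60% of visits, 80% of resident and 30% of faculty visits are in the afternoon, and adoption is 75% in the morning and 55% in the afternoon. Residents: 0.2 x 0.75 + 0.8 x 0.55 = 0.59. Faculty: 0.7 x 0.75 + 0.3 x 0.55 = 0.69. The gap is 10 points, and the chi-square test rejects in 59% of 4,000 runs, against 5% when stratified. With afternoon shares of 65% and 35% and adoption of 75% and 65%, the gap is 0.715 - 0.685 = 3 points and the rate is 11%.

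**Fewer visits.** The Study Design section reports the mother present and eligible at 91% of visits at 0-16 weeks. If that share applies, 456 x 0.91 = 415 visits, and the 70/30, 20-point cell falls from 46% to 43%.

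**Room for a model.** Status (1), sex (1), session (1), weekday (4, for five clinic days) and clinic (1) make 8 coefficients. If adoption were 89%, the Edinburgh completion rate in the brief pilot test, there would be 456 x 0.11 = about 50 non-completions, or about 6 per coefficient.

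**The case against.** A reader might infer that physician type and session are in fact entangled in these clinics, so that the planned tests will mislead. The documents do not support that. They describe a faculty practice and a supervised resident service, but not who works when. Without overlap the bias is zero and the error rate is the nominal 5%. This objection stands, and it makes the point conditional.

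The high rates also need strong overlap together with a large session gap. The only completion rates in the protocol are high: 89-90% for the Edinburgh tool, and 100% of those women for the survey on its reverse. These are completion by women; the rate for the physician section is not given and could be lower. With adoption of 92% and 86% and residents seeing 60% of visits, the false-positive rate is about 16% for afternoon shares of 80% and 30%, and about 9% for 65% and 35%.

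A reader might also infer that Aim II's quantitative results rest on these comparisons, or that training would be misdirected. Neither follows. Overall adoption and the survey measures are also planned. The training and refresher sessions are fixed in advance, and the focus groups follow the intervention. The physicians, who know their own schedule, are asked to comment on the figures, which is a partial safeguard.

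Finally, crude adoption by physician type is a valid description. It misleads only when read as influence. The protocol does state that purpose, so this answers the point only in part.

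**Conclusion.** The point holds as a conditional weakness. The plan asks what influences adoption, names only a method that cannot separate the factors, and includes no step to see whether they overlap. That gap is in the text. Whether it produces bias in these clinics cannot be determined from the documents.

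At about 456 visits with no true physician effect, the chance of a spurious physician finding is about 5% without overlap. It is about 8-16% with moderate overlap (60/40 with a 10- or 20-point session gap, or 70/30 with a 10-point gap). It is 46-59% or more with strong overlap and a 20-point gap. These figures rest on assumed overlap, adoption levels, alpha, counting period and independence of visits.

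The overall adoption rate and the primary outcome are untouched, and the plan makes no confirmatory claim for adoption. This is a minor, inexpensive improvement to a secondary aim of a pilot.

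**What to change.** In Analysis, Specific Aim II:

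1. Keep the chi-square tables, labelled as description.
2. Cross-tabulate physician status by session, weekday and clinic (CYC or PCAC), and show this to providers with the adoption figures.
3. Add one visit-level logistic model of adoption with status, sex, session, weekday and clinic. Report adjusted adoption differences with confidence intervals by average marginal predictions, as already chosen for Aims I and Ia.
4. State in advance what happens if non-completions are few: reduce the model (for example, to status and session, or a session-stratified Mantel-Haenszel comparison) or use penalised logistic regression.

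The cost is some SAP wording, a little code, and slightly wider intervals where factors overlap. There is one data requirement: the factors must be recorded jointly for each form before the stickers are removed from non-enrollees' forms. If overlap proves negligible, crude and adjusted results will be close and little is lost.

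The change does not deal with clustering of visits by physician. No physician names are collected, so that limit applies equally to the chi-square tests and to the model.
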